## ABBREVIATIONS/DEFINITIONS

### Abbreviations

AE	adverse event
ALP	alkaline phosphatase
ALT	alanine aminotransferase
ANCOVA	analysis of covariance
ANOVA	analysis of variance
AST	alanine aminotransferase
BMI	body mass index
CMH	Cochran-Mantel-Haenszel
CSR	clinical study report
DLQI	Dermatologic Life Quality Index
eCRF	electronic case report form
EASI	Eczema Area and Severity Index
EASI-50	50% reduction in EASI score
EASI-75	75% reduction in EASI score
EASI-90	90% reduction in EASI score
GPORWE	(Lilly) Global Patient Outcomes and Real World Evidence
IFN-g	interferon-gamma
IGA	Investigator's Global Assessment
IGA [0]	post-baseline IGA Score of 0 (clear)
IGA [0,1]	post-baseline IGA Score of 0 (clear) or 1 (almost clear)
IRT	Interactive response technology
Itch NRS	Itch Numeric Rating Scale
ITT	intent to treat
LDH	lactate dehydrogenase
LOCF	last observed carried forward
LY	baricitinib (LY3009104)
MedDRA™	Medical Dictionary for Regulatory Activities
MMRM	mixed effects model repeated measures
NRI	non-responder imputation
PK	pharmacokinetic
POEM	Patient-Oriented Eczema Measure

PT	preferred term
QIDS-SR16	Quick Inventory Depressive Symptomatology – Self Report 16
QOL	quality of life
SAE	serious adverse event
SAP	Statistical analysis plan
SCORAD	SCORing Atopic Dermatitis
SDTM	Study Data Tabulation Model
SOC	system organ class
TBili	total bilirubin
TEAE	treatment emergent adverse event
ULN	upper limit of the normal range
VAS	visual analog scale
WASO	Wake after sleep onset
WHODD	World Health Organization Drug Dictionary

## 1 INTRODUCTION AND OBJECTIVES

### 1.1 Introduction

The purpose of this statistical analysis plan (SAP) is to describe the analysis variables and statistical procedures that will be used to analyze and report the results from a Phase 2 study evaluating the safety and efficacy of baricitinib, a JAK1/JAK2 selective inhibitor, in patients with moderate-to-severe atopic dermatitis. This SAP is based on the amended protocol, Protocol I4V-MC-JAHG(d), which was approved on 24 June 2016.

Changes to the protocol that impact the design, the data collected, or the statistical methods and that occur after the finalization of this SAP may require amendment of the approved SAP. Similarly, changes to the planned analysis variables and/or statistical methods described in the approved SAP may also require amendment of the SAP.

The formats for the tables, listings, and figures described in this SAP are provided in a companion document. Changes to the formats of these reports that are decided after the finalization of the SAP will not require an amendment. In addition, any additional supportive or exploratory analyses requested after SAP approval will not require amendment of the SAP. These additional analyses will be described in the clinical study report (CSR).

Please see the study protocol for details about the study design, procedures, and schedule of assessments and see the electronic case report form (eCRF) for details about variables collected and their possible values.

### 1.2 Study Objectives

[Table JAHG.1](#) shows the objectives and endpoints of the study that were defined in the protocol. Additional endpoints will be defined in this SAP.

**Table JAHG.1. Objectives and Endpoints**

Objectives	Endpoints

Primary
 
 
To compare the proportion of moderate-to-severe atopic dermatitis patients achieving a 50% or greater reduction in the Eczema Area and Severity Index (EASI-50) between each baricitinib dose group (2 mg and 4 mg) and placebo when treated daily for 16 weeks
 
	
 
EASI-50 at 16 weeks
 

Secondary
 
 
To evaluate the absolute and percent change from baseline of the EASI with baricitinib compared to placebo
 
	
 
EASI at Weeks 1, 4, 8, 12, and 16
 


 
• To evaluate the mean change from baseline compared to placebo for the SCORing Atopic Dermatitis (SCORAD)
 
• To evaluate the mean change from baseline compared to placebo for the Investigator’s Global Assessment (IGA)
 
• To assess quality of life based on the Dermatologic Life Quality Index (DLQI)
 
• To assess itch based on the Itch Numerical Rating Scale (NRS)
 
• To characterize the pharmacokinetics of baricitinib in patients with moderate-to-severe atopic dermatitis
 
 
Exploratory
 
 
• To evaluate EASI response in patients based on their baseline total serum IgE
 
• To evaluate total serum IgE over the course of treatment
 
 
Exploratory (continued)
 
 
• To evaluate changes in disease activity over the course of treatment
 
• To evaluate changes in sleep quality over the course of treatment
 
• To evaluate changes in nocturnal itch patterns over the course of treatment
 
• To evaluate EASI response relative to filaggrin genotype
 
• To assess tissue biomarkers from biopsies
 
• To assess peripheral biomarkers mechanistically related to inhibition of JAK 1/2 mechanism
 
	
 
• SCORAD at Weeks 1, 4, 8, 12, and 16
 
• IGA at Weeks 1, 4, 8, 12, and 16
 
• DLQI at Weeks 1, 4, 8, 12, and 16
 
• Itch Numerical Rating Scale at Weeks 1, 4, 8, 12, and 16
 
• Plasma pharmacokinetic data
 
• EASI at Weeks 1, 4, 8, 12 and 16; baseline total serum IgE
 
• Total serum IgE at baseline, Weeks 4, and 16
 
• Patient-Oriented Eczema Measure (POEM) at Weeks 1, 4, 8, 12, and 16
 
• Change from baseline with data from a wearable actigraphy device
 
• Change from baseline with data from a wearable actigraphy device
 
• EASI-50 and filaggrin genotype data from peripheral baseline blood sample
 
• K16, Ki-67, and IL-4 will be assessed from each tissue biopsy (collected at baseline (lesion and non-lesion), at Week 4 (lesion), and at Week 16 (lesion and non-lesion))
 
• Peripheral biomarkers collected at baseline, Weeks 4 and 16
 

--	---


 
To perform subgroup assessments of response based on patient and disease characteristics
 
	
 
Ad hoc evaluation of potential prognostic and predictive disease characteristics
 

--	--

### 1.3 Determination of Sample Size

Approximately 120 patients will be enrolled using a 4:3:3 randomization scheme for placebo, 2 mg baricitinib, or 4 mg baricitinib, respectively. Assuming a drop-out rate no greater than 20%, approximately 96 patients will complete the study.

This sample size provides 90% power to detect a 35% difference in EASI-50 between placebo and either the 4-mg baricitinib using a 2-sided chi-square test with  $\alpha = 0.05$ .

## 2 General Statistical Methodology and Conventions

CHORUS will designate a provider to generate the statistical analyses detailed in this SAP. All computations for statistical analyses will be performed using SAS® software, Version 9.3 or later. All SAS programs used in the production of statistical summary outputs will be validated with independent programming prior to finalization. In addition, all program outputs will be independently reviewed. The validation process will be used to confirm that all data manipulations and calculations were accurately done. Once validation is complete, a senior statistical reviewer should perform a final review of the documents to ensure the accuracy and consistency with this plan and consistency within tables. Upon completion of validation and quality review procedures, all documentation will be collected and filed by the project statistician or designee.

Before implementation of parametric methods of analysis, the distribution of analysis variables will be examined to determine if model assumptions are satisfied. Transformations or nonparametric methods of analysis may be used if warranted. However, in some cases, nonparametric analysis may be the initially proposed method due to the expected distribution of response. Whenever alternative methods of analysis are required, the description of the new method along with the rationale for its use will be documented in the CSR.

The eCRF data for all patients will be provided in Standard Data Tabulation Model (SDTM) datasets. Any additional data listing supplied as part of the CSR will be sorted by investigative site and patient identification number, and patients will be identified in the listings by the investigator number concatenated with the patient number.

### 2.1 Randomization Schedule and Unblinding Plan

This is a double-blind study in which the patients, investigator, and study site personnel will be blinded to treatment allocation. PAREXEL International will be responsible for building the interactive response technology (IRT) system that randomly assigns study treatments to patients.

To preserve the blinding of the study, only a minimum number of Lilly personnel will see the randomization table and treatment assignments before the study is complete. A limited group may have access to unblinded treatment information to ensure the safety of patients in the study. Another small team of Lilly scientists (project statistician, statistical analyst, pharmacokineticist,

research physician, medical director, and global patient outcome scientist) will have access to the unblinded treatment information just before the last patient has completed their Week 12 visit. Their review of the unblinded data will facilitate planning of future studies. They may communicate unblinded findings to a small number of other Lilly personnel to facilitate business decisions, but not to those who are involved in the conduct of the study who would be involved in direct site contact and assessment of blinded clinical outcomes. A list of all those individuals who become unblinded prior to study completion will be maintained by the unblinded statistician. This process will ensure that data integrity is maintained while patients are still receiving blinded therapy.

Once the last patient completes Week 16, thus blinded study treatment, and all data management data activities have been completed – data entered, coding completed, and all queries resolved – the Chorus Asset Manager and Statistician will approve PAREXEL to release the randomization schedule to the reporting team. Additional Lilly personnel as well as steering committee members may also be unblinded to commence reporting of results from the treatment period. Site personnel and those Lilly personnel who are involved in the conduct of the study who would be involved in direct site contact and assessment of blinded clinical outcomes and patients will remain blinded until the study completes.

Emergency unblinding of site personnel may be performed through the IRT system. This option may be used ONLY if the patient's well-being requires knowledge of the patient's treatment assignment. All calls resulting in an unblinding event are recorded and reported by the IRT system.

## 2.2 Analysis Populations

The analyses for efficacy will be based on the intention-to-treat (ITT) principle (Gillings and Koch 1991), which seeks to preserve the benefits of randomization and avoid the issue of selection bias. The **ITT population** is defined as all randomized patients, and analyses based on the ITT population will utilize the treatments assigned at randomization.

Safety will be analyzed using the **Safety Population**. The Safety population is defined as all randomized patients who received at least one dose of a randomly assigned study treatment. Safety analyses will utilize the treatment that the patient received.

Pharmacokinetic (PK) data will be analyzed using the **PK Population**. The PK population is defined as all patients who received at least one dose of baricitinib and provided at least one post-dose PK sample. Pharmacokinetic analyses will be performed using the treatment that the patient received.

## 2.3 Handling of Dropouts and Missing Data

Analysis of the primary response endpoint, EASI-50, will include all randomized patients and utilize a non-responder imputation (NRI) analysis. All patients who discontinue study treatment at any time prior to the time point of interest, or discontinue from the study for any reason, will be defined as non-responders for the NRI analysis. Randomized patients without at least 1 post-baseline observation will also be defined as non-responders for the NRI analysis. Secondary and exploratory efficacy responder analyses will also utilize NRI analyses and all randomized patients.

For the secondary and exploratory efficacy endpoints and clinical laboratory endpoints that are collected longitudinally, a last observation analysis will be performed by carrying forward the last post-baseline assessment. These last observation carried forward (LOCF) analyses guarantee the maximum number of randomized patients who were assessed post-baseline, will be included in the analyses. In addition, for many of the efficacy endpoints, mixed effect model repeated measures (MMRM) analyses will be performed to mitigate the impact of missing data, which will be assumed to be missing at random during the study.

If only a missing or partial date for AEs or concomitant medications is available and a complete date is required for calculations, the following algorithms will be applied:

- For the start date:
  - If year, month, and day are missing then use the minimum of the patient's first visit date or the consent date.
  - If either only month or month and day are missing then use January 1.
  - If only day is missing, impute the first day of the month.
- For the end date:
  - If year, month, and day are missing then use the patient's last visit date.
  - If either only month or month and day are missing then use December 31.
  - If only day is missing then use the last day of the month.
  - Do not expand the record past the patient's last visit.

The original missing or partial date, the imputed complete date, and the indicator variable that indicates which dates were imputed will be retained in the database.

Analyses of the safety endpoints, many of which are incidence based, will include all patients in the safety population, unless specifically stated otherwise.

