## 2.7 Definition of Study Time Points

Study baseline for a patient will extend from the date of informed consent until the date of first dose of randomly assigned study medication. For efficacy, safety and background characteristics, the baseline value of a parameter will be the last measurement of that parameter during the baseline period.

The post-baseline period will start on the date of first dose of randomly assigned study medication. Study day will be defined as

$$\text{Study Day} = \text{Date} - \text{Date of 1}^{\text{st}} \text{ dose} + 1 * \text{if} (\text{Date} \geq \text{Date of 1}^{\text{st}} \text{ dose}).$$

The last part of the equation indicates that 1 is added if the date of collection/observation is greater than or equal to the date of first dose of randomly assigned study medication. This forces all post-baseline events to have a positive value and all dates prior to first dose to have a value less than 0.

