## 5 Concomitant Medications

Concomitant medications will be defined as medications, other than triamcinolone 0.1% cream, taken on or after the date of first dose of randomly assigned study treatment. This includes all medications initially taken prior to the date of first dose of randomly assigned study medication but with a stop date that is either missing or after the date of first dose of randomly assigned study medication. Those medications where the stop date is documented as prior to the date of first dose of randomly assigned study medication will be classified as prior medications. The prior medications will not be included in any summary reports.

The reporting of concomitant medications will be by WHODD preferred drug name (often the generic drug name). The report of all concomitant medications taken during the study will be prepared by treatment using the safety population, and the number and percentage of patients who received each concomitant medication will be presented.

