## 7.2 Adverse Events

AEs will be collected from the day the patient gives informed consent until 30 days after the final dose of study drug or until resolution of all serious adverse events (SAEs). Only those AEs that emerge or worsen after the date of first dose of randomly assigned study medication, i.e. treatment emergent adverse events (TEAE), will be reported. Adverse events with a missing start date will also be classified as TEAE.

Summaries of TEAE will include the number of patients with at least one TEAE for each treatment arm. When reporting by system organ class (SOC) and preferred term (PT), the reports will present the SOC in alphabetical order; while PTs within the SOC will be presented in order of overall decreasing frequency of occurrence in the combined baricitinib arms. A patient with multiple TEAEs (different PTs) coded to the same SOC will be counted only once for that SOC, but will be counted each time for different PTs within that SOC. A patient with separate events of the same PT (different start/stop dates) will be counted only once in the frequency tables for that PT.

TEAEs will be reported using the treatment that the patient received.

No statistical testing will be performed for comparisons of TEAEs.

An overview of all TEAEs will also be provided by treatment group using the types of AEs defined in the following subsections.

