## **8 Pharmacokinetic Analyses**

Venous blood samples (approximately 5 mL per sample) for the measurement of baricitinib concentrations will be drawn at baseline (pre-dose and at 15-30 minutes post-dose) and Weeks 4 (1.5-4 hours post-dose), 8 (4-8 hours post-dose), 12 (pre-dose), and 16 (30-90 minutes post-dose) post-randomization, plus at the early termination visit, if applicable. Plasma samples from patients on active treatment will be assayed for baricitinib using liquid chromatography and tandem mass spectrometry (LC/MS/MS).

Baricitinib concentrations will be summarized by treatment and time window using summary statistics (n, mean, standard deviation, coefficient of variation [CV], minimum, median, maximum, geometric mean, and geometric CV).

A population PK analysis will be performed separately and reported in a population PK report. Exposure-response relationships between the primary and select secondary efficacy endpoints and plasma exposure may also be explored.

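### Adverse events partly dated to the month or year of first dose, and Day 1 events, drop out of the TEAE tables as the rules are written; two smaller safety-counting rules also need correcting

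*SAP*

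**What the plan says.** **Partial dates.** SAP 2.3 gives two rules for incomplete AE start dates: "If only day is missing, impute the first day of the month" and "If either only month or month and day are missing then use January 1". Neither refers to first dose. A fully missing start date goes to the earlier of first visit and consent.

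**TEAE definition.** SAP 7.2 limits reporting: "Only those AEs that emerge or worsen after the date of first dose of randomly assigned study medication". It adds one override: "Adverse events with a missing start date will also be classified as TEAE". AEs are collected from consent "until 30 days after the final dose of study drug", or until serious events resolve.

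**Day 1 elsewhere.** SAP 2.7: "The post-baseline period will start on the date of first dose of randomly assigned study medication". Section 5 defines concomitant medications as those "taken on or after the date of first dose of randomly assigned study treatment". Section 8 says PK samples "will be drawn at baseline (pre-dose and at 15-30 minutes post-dose".

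**Liver tests.** Section 7.3 confines unscheduled laboratory values to listings, with one exception, for last measured values. Section 7.3.2 counts patients with any elevation after baseline in ALT, AST, total bilirubin or ALP.

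**Special-interest events.** Section 7.2.7 selects every TEAE whose preferred term contains a listed term. In that list the bracketed explanation of thrombocytopenia is a fall in red cells.

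**The concern.** Each date rule is a familiar convention, but together they work against each other. The first of a month can never be later than a first-dose date in that month, and January 1 can never be later than a first-dose date in that year. New events partly dated to those periods therefore fail the 7.2 test automatically, including those that began after dosing. An event with no date at all is counted, while one with better information is dropped.

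Day 1 events fail because 7.2 requires onset after the date of first dose, although 2.7 and section 5 place that date inside the treatment period. The section 8 sampling shows that patients are still being seen after dosing that day.

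The events lost are those closest to the start of dosing. The loss carries into the related, serious, discontinuation, severity and special-interest tables, which are all subsets of TEAEs. On the two smaller points, two programmers could produce different liver-elevation counts, and low-platelet events could be missing from the special-interest table.

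**Working it through.** There is no SAP figure to reproduce, so the rules were applied exactly as written.

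**Example.** First dose 14 July 2016 (date assumed):

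| AE start as recorded | Date used | TEAE under 7.2? |
|---|---|---|
| July 2016 | 1 July 2016 | No |
| 2016 | 1 January 2016 | No |
| 14 July 2016 | 14 July 2016 | No |
| August 2016 | 1 August 2016 | Yes |
| Fully missing | override in 7.2 | Yes |

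**Share lost.** Assumptions: onsets are evenly spread over Days 1 to N, and first dose is equally likely on any day of the year. N = 112 (16 weeks × 7) or 142 (112 + 30 days of follow-up). The 2016 calendar gives 366 dosing dates, hence 366 × 112 = 40,992 or 366 × 142 = 51,972 combinations of dosing date and onset day.

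*Day missing.* An onset is lost if it falls in the month of first dose. A month of L days contributes L(L+1)/2 such combinations.
- Seven months of 31 days: 7 × 496 = 3,472
- Four months of 30 days: 4 × 465 = 1,860
- One month of 29 days: 435
- Total 5,767, all classed as not TEAE
- 5,767/40,992 = 14.1%; 5,767/51,972 = 11.1%
- Dosing on the last day of a month: 1/112 = 0.9%; 1/142 = 0.7%
- Dosing on the 1st of a 31-day month: 31/112 = 27.7%; 31/142 = 21.8%

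*Month missing.* An onset is lost if it falls in the year of first dose.
- N = 112: 255 dosing dates keep the whole window in the year. 255 × 112 + (1 + … + 111) = 28,560 + 6,216 = 34,776; 34,776/40,992 = 84.8%
- N = 142: 225 such dates. 225 × 142 + (1 + … + 141) = 31,950 + 10,011 = 41,961; 41,961/51,972 = 80.7%
- By dosing date the share runs from 0.7-0.9% (31 December) to 100%. It is 100% for 255/366 = 70% of dates (N = 112) or 225/366 = 61% (N = 142).

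*Day 1, fully dated.* All are lost: 1/112 = 0.9% or 1/142 = 0.7% of the window.

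The 2015 and 2017 calendars change these averages by no more than 0.1 percentage point.

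**Changing only the comparison to on or after.** This rescues day-missing events only for dosing on the 1st of a month (366 combinations), and month-missing events only for dosing on January 1 (N combinations).
- Day missing: 5,767 − 366 = 5,401, which is 13.2% or 10.4%
- Month missing: 34,776 − 112 = 34,664 (84.6%); 41,961 − 142 = 41,819 (80.5%)

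With a first-dose floor added as well, none of the 51,972 on-treatment onsets is lost, whether fully dated, day-missing or month-missing.

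**Liver tests.** Suppose ALT exceeds 3×ULN only at an unscheduled test and a Week 16 value exists. Under 7.3 that value appears in a listing only; under 7.3.2 the patient is counted.

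**Special-interest match.** Matching preferred terms against the 7.2.7 list finds *Thrombocytopenia*, misses *Platelet count decreased*, and picks up *Red blood cell count decreased*.

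**The case against.** - **The override in 7.2 may be meant to cover partial dates.** If so, that loss disappears, and the override does suggest a wish to count events that cannot be dated. But 2.3 names missing and partial dates separately, and 7.2 repeats only the first. At best the text supports two different counts.
- **Worsening is a second route.** An event recorded as worsening after first dose still qualifies. This stands, so the exclusion concerns new-onset events.
- **The month-missing average hides a very wide range and may describe few events.** This stands. The average depends on year-round dosing, and with regular visits and query resolution before unblinding, events dated by year alone may be rare.
- **Day 1 is shared.** SAP 2.7 also runs baseline up to the first-dose date, and dates alone cannot separate events before and after the dose. True, but the post-baseline period and concomitant medications both include that day, and the TEAE rule does not.
- **The specific liver rule should override the general one.** This is a reasonable reading. However, 7.3 names a single exception, and the liver counts are not it.
- **The bracketed wording may not be a search term.** *Platelet count decreased* is then still missed. It would still appear in the main TEAE table, low platelets would show in the laboratory shift tables, and a red-cell event would appear under its own name.
- **Limited consequence.** The rules are the same in every arm, TEAEs are not tested, all SAEs are listed and original partial dates are kept. All of this stands.

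**Conclusion.** The point holds. Read as written, 2.3 and 7.2 remove every new-onset AE partly dated to the month (day missing) or year (month missing) of first dose, and 7.2 alone removes Day 1 onsets. On the even-spread assumptions, the loss is 11.1-14.1% of day-missing and 80.7-84.8% of month-missing on-treatment events; by dosing date it ranges over 0.7-27.7% and 0.7-100%. The SAP does not say how many AEs are partly dated, so the share of all AEs cannot be given. The error is an undercount of early events; no difference between arms is shown and no efficacy conclusion changes.

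The liver-test conflict and the thrombocytopenia wording are also real but smaller, and neither can be sized from the SAP. All three should be corrected before the tables are programmed.

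**What to change.** 1. **SAP 7.2:** define a TEAE as an event with onset or worsening on or after the date of first dose.
2. **SAP 2.3:** for AEs, impute a partial start date to the date of first dose when the known parts are compatible with that date and the end date is not earlier; otherwise keep the present rules. Changes 1 and 2 are both needed.
3. **SAP 7.3 and 7.3.2:** state that counts of patients with any liver-test elevation after baseline use scheduled and unscheduled values.
4. **SAP 7.2.7:** replace the red-cell explanation of thrombocytopenia with platelet count decreased.

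The cost is SAP wording and small programming changes. The trade-off is that some events that began before dosing, on Day 1 or with a partial date, will be counted as TEAEs. AEs are collected from consent, so this includes screening events in the same month or year with no earlier end date. Their number cannot be estimated from the SAP, but the retained original dates and imputation indicator allow them to be identified.
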